5.1 Pilot phase

The pilot phase will occur over an estimated 3-month period in small number of facilities in each country whilst the pre-intervention assessment is occurring in the pre-post study facilities. It will serve to refine the intervention package if necessary, including the approach to training, supervision, caregiver engagement and guidance on where to use the devices within the care process. This refined package will then be implemented in the remaining facilities involved in the TIMCI project.

The pre-post study dataset will be collected from these pilot facilities and will be used for exploratory analysis in comparison with data from the main pre-post study. We will also collect SPA, process mapping and time-flow data and qualitative data (from interviews with caregivers, healthcare providers and key stakeholders; possibly informal group discussions, feedback from post-training assessments by PATH). These studies will aid understanding of implementation processes, mechanisms and context. Emphasis will be placed on exploring acceptability, and barriers and facilitators to implementation to inform fine-tuning and adaptations of the intervention.

Concurrently, we will pilot the research instruments and processes and refine if necessary, including eligibility screening, participant information and consent, and data collection tools.

5.2 Quasi-experimental pre-post study

A quasi-experimental pre-post study, comparing clinical care of children attending primary care facilities in a pre-intervention (baseline period) with those attending facilities following introduction of the intervention (intervention period). The 6 – 8 month baseline period is followed by a 9 – 12 month intervention period to allow for evaluation of change over time

from introduction of intervention and for some seasonal overlap in pre- and post-intervention periods.

5.3 Service provision assessment

This periodic assessment of service delivery will follow the approach of the Demographic and Health Surveys (DHS) Program Service Provision Assessment (SPA) (facility assessment, healthcare provider interview, sick child observation protocol and caregiver interview),⁴⁰⁻⁴² modified to focus on child health, pulse oximetry and CDSA use and incorporate additional quantitative and qualitative questions covering factors associated with child mortality and health-seeking behaviour, as well as patient-centred outcomes including experience of care.

We will conduct cross-sectional surveys at a stratified sample of facilities at baseline and during early and late intervention periods in order to assess differences over the course of implementation and with varying burden of disease in different seasons. Stratification is based on rural / urban location, facility type, and, where applicable, district and altitude. On the days of the surveys, we will conduct an abbreviated facility assessment, administer a questionnaire to all providers consulting children under five, and a modified 'sick child' observation and exit interview on all eligible children attending the facility.

5.4 Facility-based process mapping and time-flow study

Prior to intervention, we will develop a basic process map defining the common steps in the care pathway of sick children in primary care facilities in each country (adapted to facility type). The map will be reviewed and refined through informal discussions with staff and non-participant observation at a sample of facilities (including on whether specific processes have been introduced or changed as a result of COVID-19). Time-flow data will be captured for discrete steps in the care process through observation of a sample of children attending the facility, from arrival through to consultation (including on use of the devices), to departure from the facility. Non-participant observation will focus on understanding rationale for care processes and when and why deviation from the standard pathway may occur.

This pre-intervention map will be adapted to incorporate pulse oximetry and CDSAs through discussions with staff and observations in the pilot facilities to understand the impact of the intervention on care processes (including on time) and on patient-provider interactions, and inform refinement of the intervention strategy if necessary. After roll-out of the intervention, this will be repeated both early and late in the intervention to understand changes in care processes and time with the refined intervention package, and adaptations that may have occurred as a result of provider preferences (or as a result of other changes to care processes external to the TIMCI project). This will also generate information on whether the intervention has been normalised into care processes over the longer-term in order to understand sustainability and inform the package for scale. Time-flow data will also be used in the cost and modelled cost-effectiveness study.

5.5 Healthcare provider perceptions of the intervention

We will conduct semi-structured in-depth interviews (IDIs) and possibly focus group discussions (FGDs) with clinical vignettes with a purposive sample of healthcare providers working in intervention facilities. IDIs (and informal group discussions) will be conducted at the pilot facilities to inform intervention refinement. IDIs and possibly FGDs will be conducted over the course of the intervention to understand changes in perception of the intervention over time and reasons for early and late adoption. In Kenya and Senegal only, IDIs will also take place pre-intervention for comparison. FGDs will be based around clinical vignettes to facilitate discussion of experiences with the devices (including usability, practicality and design) and on quality of care and acceptability of tools without causing unwanted disclosure, or bias due to self-stigmatization or self-censorship. IDIs, which may include vignettes, will focus particularly on the individual experience with the introduction of the intervention and over time; the acceptability of the intervention; mechanisms, processes and contexts leading to behaviour change and identifying barriers and facilitators for intervention success.

5.6 Caregiver perceptions of the intervention and health-seeking behaviour

Semi-structured IDIs, walking interviews resulting in case studies (CS) and FGDs will be conducted with a purposive sample of caregivers who have attended study facilities. IDIs and FGDs will be carried out at the household and respective community level.

IDIs (and informal group discussions where required) will be carried out with caregivers attending pilot facilities to inform intervention refinement. IDIs, walking interviews and FGDs will be conducted with caregivers attending intervention facilities over the course of the implementation period to understand changes in perception of the intervention over time and behaviour change. In Kenya and Senegal only, IDIs will also take place pre-intervention for comparison. The IDIs, walking interviews and FGDs will focus on aspects of the quality of care and acceptability frameworks, as well as health-seeking behaviour and decision making, incorporating a realist approach. Walking interviews will delve into greater detail on decision-making on and experience of referral.

Classical FGDs will be paired with focus groups incorporating method acting (i.e. adaptation of interactive performance) structured in a three-step approach including verbalized senses and experiences, embodied images and performance, using photo- and or video-recording. Method acting is particularly useful when conducting focus groups with participants who have low health literacy or in groups where hierarchy between participants predominates, and can enable empathetic associations, linking knowledge, attitudes and behaviour to personal lived experience.

Walking interviews will be conducted with a purposive sample of caregivers having received referral advice and after their visit at an intervention facility allowing for case studies. Walking

interviews will use an explorative theme catalogue focusing on the care seeking pathway and decision-making. When accompanying the caregiver, the pathway will be tracked by the data collector (e.g. by using a mobile device and GPS data). Hand-written notes and GPS coordinates from qualitative data collected will be used for mapping of care seeking pathways.

Participants with a particularly interesting or divergent view in focus group discussions with health care providers or caregivers might be approached for follow-up IDIs.

Qualitative data collection is exploratory in nature; time points in data collection are preliminary. Final time points will depend on the preliminary analysis of qualitative data and findings throughout the data collection. Therefore the studies planned may require a closer follow-up or data collection at additional time points (e.g. mid phase of the intervention).

5.7 Stakeholder perceptions and project data review

This will incorporate key-informant interviews (KIs) with selected stakeholders at global, national, subnational and local level with perspectives on implementation, policy and research. Stakeholders will include those internal (i.e. project stakeholders, e.g. PATH) and external (i.e. non-project stakeholders e.g. Ministry of Health, community, other organisations) to the project, either directly involved in implementation or affected by implementation. This includes, but may not be limited to: selected International Advisory Group members, Unitaid and WHO representatives, PATH headquarters staff, national policy makers, members of district health management teams, health facility managers, community leaders, national and local PATH implementation staff and research staff. The KIs will be conducted during the pilot phase, to understand perspectives at the start of implementation, and during late intervention, to gain reflections into implementation over time and to inform a package for scale. In Kenya and Senegal only, KIs will also be conducted in the pre-intervention phase to understand health care provision prior to implementation.

These interviews will be complemented by electronic surveys of selected project informants and a structured review of key documents including PATH project reports (including on changes as a result of COVID-19), minutes and M&E data (e.g. on training evaluation or maintenance and replacement of devices) for each country. It will primarily focus on the processes, mechanisms and context (i.e. MRC process evaluation criteria) of implementation including adaptations made.

In each country, PATH project data, along with routine Health Management Information Systems (HMIS) data, and anonymised data from clinical consultations with the CDSA routinely entered by healthcare providers will be assessed for all facilities and administrative regions where the project is running (i.e. both study facilities and non-study facilities) to draw inferences on the wider project implementation.

5.8 Cost and modelled cost-effectiveness study

The economic evaluation will involve a cost analysis and modelled cost-effectiveness using direct health system costs in which financial and economic costs will be assessed. The scope of the costing will cover only intervention costs and not research-based costs, and will include costs incurred by the health system as well as estimated direct costs paid out of pocket by the households to the health system. It is important to note that this cost methodology is not comprehensive. It does not include the indirect costs incurred by the consumer (patient) e.g. the caregiver's time or transport costs. Rather, it focuses exclusively on the provider's direct costs, whether borne by the health system or paid out of pocket by the patient's household.

The approach that has been taken in applying this methodology has been to capture what is thought to be the "most likely" cost scenario, on average. In identifying this "most likely" cost scenario, effort will be made to supplement the analysis with a discussion about factors that influence the level of costs (e.g. the number of trainees per training, or the frequency of supervision) so as to provide a type of sensitivity analysis of the robustness of the estimates. Cost scenarios will also guide possible future programme scale up. The cost resources for each cost centre might differ across the three countries. For instance, at some facilities laboratory tests or some treatments may not be available, and patients have to be referred elsewhere: we will have to take account of these differences.

Research-based costs are excluded to enable the costing to provide guidance on future replication and potential scale up of the intervention. Full and incremental costing involving an activity-based and ingredient-based approach will be used. When available, effectiveness data will be combined with the cost data and cost per DALY averted will be estimated as outlined in 7.3.3. The costing and modelled cost-effectiveness will use a 12-month time frame and a 3% discount rate. Where applicable, discount rates will be adjusted to prevailing rates at country-level.

6 Participants, interventions, and outcomes

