Service provision assessments, at baseline, early and late intervention implementation, will assess: adherence to IMCI (or national guidelines) and device guidelines (during intervention phase), including proportion of: caregivers asked about all three danger signs; caregivers asked about all main symptoms; children with cough or difficulty breathing in whom a respiratory rate is counted for a minute and (where applicable) in whom a pulse oximetry reading is attempted, conducted correctly, obtained at first attempt or at repeated attempts; and proportion of children in whom CDSA is used and recommendations are adhered to. Furthermore, correctness of classification and treatment (as far as is possible with available information), and other indices of quality of care will be assessed. Facility and healthcare provider factors associated with health and quality of care impact and intervention uptake will be assessed.

Facility-based process maps and associated non-participant observational data will be described and compared between baseline and early and late intervention periods. Time (in minutes) will be compared (pre, early and late intervention) for total in clinic; in consultation; and on use of devices, and any other relevant single steps of the care process. Comparison will be made using mean (if parametric) or median (if non-parametric).

Qualitative enquiry with healthcare providers and caregivers will primarily focus on service provision, the participant response to the intervention and acceptability of devices, with exploration of change in perceptions, attitudes and behaviour over time. With caregivers, we will also explore experience of care and care-seeking behaviour through IDIs and walking interviews.

The sub-study of stakeholder perceptions, surveys and project data review will primarily focus on the processes, mechanisms and context (i.e. process evaluation criteria with focus on fidelity, dose, reach, context and adaptation) of implementation including adaptations made.

6.4.3 **Cost and modelled cost-effectiveness study**

- ξ Full implementation cost of the intervention per focal country (cost to health system as well as direct costs paid by the household to the health system)
- ξ Cost per child assessed using pulse oximetry devices and CDSA per country compared to without these supports.

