7.1.4 Cost and modelled cost-effectiveness study

Cost data collection will occur pre- and during intervention as shown in **Fig. 3**.

Definition of costs using an activity-based approach

An activity-based approach will be explored using available cost data. Specific activities in the intervention will be allocated to different cost centres. In order to provide cost estimates that will be as managerially-, policy- and programmatically-relevant as possible, the cost analysis will adopt this approach as this separate research costs from the main programme implementation costs. The focus will be on those costs that are expected to change with the introduction of pulse oximetry and CDSAs. Costs including utilities and large equipment costs will remain the same with or without the introduction of pulse oximetry and CDSAs.

To apply the activity-based approach, we will identify specific activities that are to be costed. These will be referred to as "cost centres" (See **Tab. 6**). Cost centres are a way in which the resources used to produce the intervention activities—and the costs of those resources—are grouped. Cost centres are defined in such a way that:

- ξ The sum of the cost centres is comprehensive—including all the resources used to produce each and every activity of the program—and together, the entire program, and
- ξ They are mutually exclusive—thus avoiding double counting any of the resources used to provide the program.

It is important to note that this cost methodology is not comprehensive. As described in 5.8, it does not include the indirect costs incurred by the consumer (patient) e.g. the caregiver's time or transport costs. Rather, it focuses exclusively on the provider's direct costs, whether borne by the health system or paid out of pocket by the patient's household. The cost resources for each cost centre may differ between each country according to availability of services.

Tab. 6. Activity-Based Cost Centres of the TIMCI programme

1	Training cost for staff involved in delivering the programme:
	
- Consumable costs (including where applicable stationary, and other consumables)- Personnel costs- Overhead costs (including where applicable, rent for training venue, administrative costs, per diems and transport costs, and other overheads)
2	Delivery of intervention

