	
- Annualized¹ fixed/equipment costs (including pulse oximetry device and CDSA tablet costs)- Consumable costs (including medicines, diagnostic tests, and other consumables)- Personnel costs
3	Out of pocket costs
	
- Any out of pocket costs paid by patients' households to the health system to access care and prescribed treatment will be collected, including resources purchased outside the facility due to unavailability in the facility. However, care not prescribed by facility healthcare professionals will not be included.

1. Since costing needs to account for both capital and recurrent costs, annualizing capital costs (i.e. calculating the annual value of a capital item) is the easiest way of combining capital and recurrent costs meaningfully. Annualizing capital cost is based on three pieces of important information: the initial purchase price of the item, its expected useful life, and a discount rate

Sources of cost data

Personnel and procurement units of the organisations involved in the TIMCI intervention, especially through different local PATH offices and sampled facilities will be sourced for the cost data. Centrally available databases will be used to estimate personnel and consumable (including medicines and diagnostics) costs where available.

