	Consumables	Disposable items used per child per intervention	Quantity of consumables used per child	Medical personnel at health facility	Market prices	Centrally from government databases and complemented with provider's

						procurement department
	Equipment/ Capital (incurred every few years)	Pulse oximetry devices, tablets etc	Annualised cost of items	Interview, observations, and timing	Replacement prices	Provider's financial syndicate office
	Out of pocket costs	All out of pocket costs paid by patients' households to the health system for fever management	Direct fees and charges paid by households to health systems	Cost borne by households	Financial cost	Cost data collected from health system administrative records; information from interview of senior non- medical personnel

Definitions of types of costs and data to be collected

Staff time: For each activity within the TIMCI project, the responsible staff member involved with the activity will be identified. Secondly the time involved will be ascertained from the time-flow study and quantified. Supervision costs will similarly be estimated.

Consumables: The type and quantity of medicines, diagnostic tests and consumables used for each activity will be identified. In addition, unit costs of each consumable item will be obtained (for example the cost of an oxygen cylinder) and the size of unit (the time average spent on oxygen per patient).

Equipment: All equipment used for each activity will be identified and the price for which it was purchased. For the equipment costing, the lifespan for the equipment (usually between 3 – 5 years for smaller items including electronic tablets and pulse oximetry devices) will be obtained and annualized. Annualization will follow the cost recovery methodology where item cost, life span, and a defined interest rate is used to estimate the annual cost of an item. For equipment that is shared with other activities, the time spent per consultation will be obtained as a percentage of total time spent using each equipment and used to calculate the cost associated with the intervention after annualization. For donated equipment, market price information will be sought.

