Equipment inventories and training records will be used to collect retrospective costs. Time spent by staff on consultations with children 0 – 59 months of age will be collected from data obtained in the time-flow study. Time costs will then be determined by combining staff annual salaries obtained from government sources and/or payroll offices with time spent in consultations with children. Where applicable, this personnel cost will be disclosed only to the principal researcher without the identity of staff involved. Consumables used will be examined

to determine the unit cost of each consumable, while equipment will be annualized to determine their unit costs.

All capital and start-up costs will be annualised using an appropriate length of life and discount rate. Out of pocket payments to health systems borne by households will be estimated to capture all health system costs. These costs might vary across different settings since there might be flat rates in one setting and a varied fee schedule in another. Hence, the cost data collection for out of pocket payments will be country specific. The cost of hospital referrals where applicable, will also be estimated from interviews with senior healthcare professionals at the hospital level. Data will be captured and analysed in an excel workbook.

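### Delivery costs and household payments are summed as separate cost centres, but as defined they overlap and nothing nets fees off, so cost is overstated wherever households pay

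*Protocol*

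**What the plan says.** The economic outcome in Protocol 6.4.3 is the full implementation cost per country, described as "cost to health system as well as direct costs paid by the household to the health system". Section 5.8 uses similar additive wording, "costs incurred by the health system as well as estimated direct costs paid out of pocket by the households to the health system", but also describes the provider's direct costs as counted "whether borne by the health system or paid out of pocket by the patient's household", which reads as one set of costs divided by payer.

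Section 7.1.4 gives the aggregation rule. It begins "The sum of the cost centres is comprehensive" and adds that the centres are mutually exclusive, "thus avoiding double counting any of the resources used to provide the program".

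The centres are then defined as follows:

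- **Centre 2, delivery (Tab. 6).** It contains device costs, personnel, and "Consumable costs (including medicines, diagnostic tests, and other consumables"). Tab. 7 values staff at gross remuneration, and consumables as quantity per child at market prices. The text on sources of cost data takes volumes of tests and treatments from what was prescribed.
- **Centre 3, out of pocket (Tab. 6).** It covers what households pay for care and prescribed treatment, including items bought elsewhere because the facility had none. Tab. 7 measures it as "Direct fees and charges paid by households to health systems".

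The definitions after Tab. 7 add: "Out of pocket payments to health systems borne by households will be estimated to capture all health system costs". They also note that charging differs between settings. Section 7.3.4 collates the components and divides the total by the number of children. The SAP does not cover the costing.

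**The concern.** A fee that a household pays the facility for a drug, test or consultation helps to finance inputs that centre 2 has already valued in full. It is a transfer, not a further resource. If both centres are summed, that part of the cost enters twice. The mutual-exclusivity statement forbids this, but the definitions that follow do not achieve it, and nothing in 5.8, 7.1.4 or 7.3.4 treats fees as revenue or limits centre 3 to items absent from centre 2.

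Full implementation cost, cost per child and cost per DALY averted are the stated economic outcomes and are meant to inform scale-up. An error that depends on local fee levels affects the level of these figures and also the comparison between countries.

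**Working it through.** The protocol states no cost total, unit price or fee level, so there is no figure to reproduce. The check is an accounting identity.

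**Inputs**

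- R: input value of the items in centre 2 for which households also pay. Not given.
- f: share of R that households pay and that is recorded again in centre 3. Not given; the whole range 0 to 100% is shown.
- T: costs without a matching fee, such as training and donor-funded devices. Not given.

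**1. Level of cost**

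Sum of centres as written: T + R + fR. Each resource valued once: T + R. The excess is fR, which is a fraction f of the overlapping items and fR/(T + R) of the total. The second fraction is smaller than f whenever T is above zero (and f is not zero).

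For R = 100:

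| f | Sum as written | Valued once | Excess on overlapping items |
|---|---|---|---|
| 0% | 100 | 100 | 0% |
| 10% | 110 | 100 | 10% |
| 25% | 125 | 100 | 25% |
| 50% | 150 | 100 | 50% |
| 75% | 175 | 100 | 75% |
| 100% | 200 | 100 | 100% |

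**2. Prescribed items bought outside the facility, price p**

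- If centre 2 volumes are everything prescribed, the item enters centre 2 at p and centre 3 at p: 2p in all.
- If centre 2 volumes are facility-supplied items only, it enters centre 3 alone: p, which is correct.

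The text in 7.1.4 points to the first reading. Tab. 7 speaks of quantities used, which could support the second.

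**3. Direction of bias in incremental cost**

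The sample-size figures in 6.6.1 serve here only as an illustration. They are detectable differences, not predicted effects or costing inputs.

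- Antibiotics: 0.60 x 0.18 = 0.108 fewer courses per child if the 18% is relative. At a course price of 1, the reported saving is 0.108 x (1 + f): 0.108, 0.162 and 0.216 for f = 0, 50% and 100%. If 18 percentage points is meant, the figures are 0.18, 0.27 and 0.36.
- Referral: 0.045 - 0.030 = 0.015 more referrals per child. With input value h per referral and household share g, the reported extra cost is 0.015 x h x (1 + g).

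Excess in incremental cost = 0.015gh - 0.108fp, where p is now the price of an antibiotic course. This is negative (favours the intervention) only if gh is below 7.2fp, since 0.108/0.015 = 7.2. On the percentage-point reading the multiple is 0.18/0.015 = 12. None of f, g, h or p is in the documents. A flat consultation fee that is the same before and after cancels from the increment per child, although it still raises the level.

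**4. Comparison between countries**

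For the overlapping items, the reported cost ratio of country A to country B is the true ratio times (1 + f_A)/(1 + f_B). With f_A = 0 and f_B = 50%, the factor is 1/1.5 = 0.67. With equal shares it is 1.

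**The case against.** The protocol does not ignore the problem. It declares the centres mutually exclusive for this very reason, and 5.8 describes provider costs by payer. Estimating household payments so as to capture all health-system costs can mean completing a total rather than adding to it. Tab. 6 lists centres, and Tab. 7 lists sources and valuations; neither shows a total. Section 5.8 also promises both financial and economic costs, and Tab. 7 labels out-of-pocket payments as financial, so the analyst may intend to keep the two apart. On this view the protocol lacks a detail and no error has been made.

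What stands is the intent: the authors want each resource counted once, and a careful analyst may do so. But the intent contradicts the definitions and does not repair them. The centres are said to be summed, 6.4.3 joins the two components in one outcome, and no rule says how a fee for an item already in centre 2 is to be handled.

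Two stronger readings are tempting. A reader might infer that implementation cost is doubled. It is not: the excess is limited to items with fees and to the share paid, and doubling of even those items needs households to pay the full price. A reader might also infer that the error favours the intervention, because savings on drugs would be inflated while devices and training are counted once. The documents do not support that, because household payments for additional referrals or admissions would be inflated as well.

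**Conclusion.** The protocol contradicts itself on a stated economic outcome: the centres are declared mutually exclusive but defined so that they overlap, with no netting rule. The missing rule can be read directly from the text. The size cannot: it rests on f, for which the documents give no value, and the full range from step 1 remains open. It also assumes that the analyst follows Tab. 6 and Tab. 7 literally; it is not shown that any total has been or will be computed that way. Training and donor-funded devices would be affected only if fees recover them. The between-country comparison is distorted to the extent that household shares differ, which the protocol's own remark on differing fee schedules makes plausible. The point should be settled before the cost data are aggregated.

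**What to change.** In 5.8, 6.4.3, Tab. 6 and Tab. 7, state that each resource is valued once. Then either report household payments to facilities as a breakdown of who pays, outside the sum, or deduct fee revenue from health-system cost before adding them.

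Define centre 2 volumes explicitly, in one of two ways:

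- all prescribed items, in which case outside purchases are not added again; or
- facility-supplied items only, in which case prescribed items bought outside are added through centre 3.

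This choice matters, because adding outside purchases to a centre 2 built on prescribed volumes would itself double count. Under the second option, also confirm that outside purchases can be identified: Tab. 7 draws out-of-pocket data from administrative records and an interview with senior non-medical staff, and it is not clear that these capture them.

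The cost is a few sentences, a note to two tables and a change in the workbook. The reported total may be lower.
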